2.3.2. Secondary Safety Endpoint(s)

The secondary safety endpoints are:

• All bleeding events occurring during the Main Treatment Period: from the date of first dose of study drug to the Month 3 Visit, or to the date of last dose of study drug plus 3 days if study treatment is discontinued, whichever is earlier.

- A combination of major and CRNM bleedings from the day after Month 3 Visit to the date of the last dose of study medication plus 30 days for subjects who participate in the Extension Period.
- All bleeding events from the day after the Month 3 Visit to the date of last dose of study medication plus 30 days for subjects who participate in the Extension Period.

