2.3.3. Secondary Efficacy Endpoints

The secondary efficacy endpoints are:

- The combination of symptomatic TE in the systemic arterial or venous pathways including DVT, PE, stroke, intracardiac thrombus, SEE, and MI, and asymptomatic intracardiac thrombus identified by cardiac imaging, that occur from randomization to the Month 3 Visit.
- Deaths as a result of TE that occurs from randomization to the Month 3 Visit.
- All-cause mortality from randomization to the Month 3 Visit.
- The combination of symptomatic TE in the systemic arterial or venous pathways and asymptomatic intracardiac thrombus identified by cardiac imaging, which occur from the day after the Month 3 Visit to the date of the last dose of study drug plus 30 days for subjects who participate in the Extension Period.
- Deaths as a result of TE that occurs from the day after Month 3 Visit to the date of the last dose of study drug plus 30 days for subjects who participate in the Extension Period.
- All-cause mortality from the day after the Month 3 Visit to the date of the last dose of study drug plus 30 days for subjects who participate in the Extension Period.

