5.2.4.1. To Initiate Edoxaban Treatment at Randomization

For subjects without prior anticoagulant therapy, edoxaban may be started the day of randomization (Day 1).

For subjects who received VKA treatment prior to randomization and are randomized to edoxaban, VKA treatment will be discontinued the day before randomization and edoxaban dose will be initiated when an INR \leq 2.5 is reached. It is per Investigator's discretion based on his/her local practice and on the subject's underlying cardiac disease to consider if heparin bridging is necessary during this period. Heparin bridging will be provided by the Investigator.

If heparin bridging is used, edoxaban will be started as below:

- 1. In case of bridging with a LMWH twice a day regimen, edoxaban dosing will start 12 ± 3 hours after the last LMWH dose
- 2. In case of bridging with a LMWH once a day regimen, edoxaban dosing will start 24 ± 3 hours after the last LMWH
- 3. In case of bridging with a UFH regimen, edoxaban dosing will start 4 ± 1 hour after the last UFH dose

5.2.4.2 Transition SOC-Treated Subjects during the Main Treatment Period to Edoxaban in the Extension Period

For subjects who received VKA treatment edoxaban dosing will be initiated when an INR \leq 2.5 is reached. This may occur as early as next day of the Extension Period.

If the subject was originally randomized to UFH or LMWH, edoxaban will be started as below:

1. In case of LMWH twice a day regimen, edoxaban dosing will start 12 ± 3 hours after the last LMWH dose

- 2. In case of LMWH once a day regimen, edoxaban dosing will start 24 ± 3 hours after the last LMWH
- 3. In case of UFH regimen, edoxaban dosing will start 4 ± 1 hour after the last UFH dose

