11. STATISTICAL METHODS

11.1. General Statistical Considerations

All efficacy analyses will be based on the modified intention-to-treat (mITT) Analysis Set and will be performed based on the treatment group assigned at randomization.

Safety analysis will be performed using the Safety Analysis Set. Subjects will be analyzed according to actual treatment received.

All analyses for the Extension Period will be based on subjects who participate in the Extension Period and take only edoxaban in the Extension Period, in the specified analysis set, and will be summarized for the edoxaban treatment group. Data listings will be prepared for subjects who are randomized to the SOC arm, participate in the Extension Period, and do not switch to edoxaban right after the Month 3 Visit.

All confidence intervals will be descriptive and will be two-sided 95% confidence interval (CI), unless otherwise specified.

Unless otherwise specified, the baseline value of an efficacy variable for a subject is the last nonmissing measurement before the randomization, and the baseline value of a safety variable is the last non-missing measurement before the first dose of the study drug.

In general, missing data will not be imputed for the purpose of data analysis. No visit windows will be used for analysis.

Continuous variables will be summarized by the number of observations, mean, standard deviation, median, and minimum and maximum values. Categorical variables will be summarized using frequency counts and percentages. Summary statistics will be presented by treatment group.

There is no formal statistical interim analysis planned. However, after the first 50 subjects enrolled in the edoxaban treatment group and 25 subjects enrolled in the SOC treatment group complete the first 3-month treatment period, an interim assessments by IDMC of safety endpoints will be performed to allow for enrollment of subjects <1 year of age into study.

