11.4.1.1. Secondary Efficacy Analysis

The TE stated in this Section, include symptomatic thrombi in the systemic arterial or venous pathways (DVT, PE, stroke, SEE, intracardiac thrombus, and MI), and asymptomatic intracardiac thrombus identified by cardiac imaging.

The following secondary efficacy endpoints will be summarized by treatment group using incidence, and annualized event rate for both the Main Treatment Period and the Extension Period, as well the rate difference between edoxaban and the comparator with the corresponding 95% CI for the Main Treatment Period. The incidence of each component will also be summarized by treatment group. This analysis will be based on CEC adjudicated results.

- The combination of symptomatic TE in the systemic arterial or venous pathways including DVT, PE, stroke, SEE, intracardiac thrombus, MI, and asymptomatic intracardiac thrombus identified by cardiac imaging that occur from randomization to the Month 3 Visit.
- Deaths as a result of TE that occurs from randomization to the Month 3 Visit.
- All-cause mortality occurring from randomization to the Month 3 Visit.
- The combination of symptomatic TE in the systemic arterial or venous pathways including DVT, PE, stroke, SEE, intracardiac thrombus, and MI, and asymptomatic intracardiac thrombus identified by cardiac imaging, which occur from the day after the Month 3 Visit to the date of last dose of study drug plus 30 days for subjects who participate in the Extension Period.
- Deaths as a result of TE that occurs from the day after the Month 3 Visit to the date of last dose of study drug plus 30 days for subjects who participate in the Extension Period.
- All-cause mortality which occur from the day after the Month 3 Visit to the date of last dose of study drug plus 30 days for subjects who participate in the Extension Period.

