11.4.3. Safety Analysis

11.4.3.1. Analysis of Bleeding Events

The primary safety endpoint is the composite of major and CRNM bleeding events that occur during the Main Treatment Period: from the date of first dose of study drug to the Month 3 Visit, or to the date of last dose of study drug plus 3 days if study treatment is discontinued, whichever is earlier. This analysis will be based on CEC adjudication results.

The time to major or CRNM bleeding occurring during the Main Treatment Period will be compared between treatment groups for subjects in the Safety Analysis Set, using the Cox proportional hazards regression model with treatment group, concomitant usage of aspirin at baseline, and underlying disease (Kawasaki disease, Fontan surgery, heart failure or Other) as covariates. Hazard ratio between edoxaban and SOC treatment group will be calculated with corresponding 95% CI. The incidence, annualized event rate, and rate difference between edoxaban and SOC treatment groups will also be calculated.

In addition, incidence, annualized event rate and rate difference between edoxaban and SOC treatment groups with corresponding 95% CI will be calculated for following endpoints for Safety Analysis Set for the Main Treatment Period. Incidence and annualized event rate will also be calculated for the following endpoints occurring from the day after Month 3 Visit to date of last dose of study drug plus 30 days in the Extension Period.

- Major and CRNM bleeding event combined
- Major bleeding event
- All bleeding event (major, CRNM, and minor bleeding combined)

The above 3 categories of bleeding endpoints will also be summarized for the periods and subjects below:
- Incidence, annualized event rate, and rate difference will be calculated for events occurring from the date of first dose of study drug to the date of last dose of study drug plus 30 days for subjects who do not participate in the Extension Period.
- Incidence and annualized event rate will be calculated for events occurring from the day after Month 3 Visit to the data of last dose of study drug for subjects who participate in the Extension Period.

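### Extension results open at the Month 3 Visit rather than at first edoxaban dose, and pool new edoxaban starters with children already three months on it, with no clear split by randomised arm

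*Combined protocol and SAP*

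**What the plan says.** **Window.** Section 11.4.3.1 gives incidence and annualised rates for bleeding "endpoints occurring from the day after Month 3 Visit to date of last dose of study drug plus 30 days in the Extension Period". Section 2.3.2 has the same start ("All bleeding events from the day after the Month 3 Visit to the date of last dose of study medication plus 30 days"), as do Section 2.3.3 ("Deaths as a result of TE that occurs from the day after Month 3 Visit to the date of the last dose") and Section 11.4.1.1 ("which occur from the day after the Month 3 Visit to the date of last dose of study drug plus 30 days for subjects who" take part in the Extension). The additional analyses in Sections 11.4.1.2 and 11.4.3.1 that stop at the last dose keep this start. No Extension window begins at the first edoxaban dose.

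**Population and display.** Section 11.1 limits Extension analyses to subjects who "participate in the Extension Period and take only edoxaban in the Extension Period", and the results "will be summarized for the edoxaban treatment group". SOC-randomised subjects who do not move to edoxaban *right after* the Month 3 Visit go into data listings. That interval is not given in days.

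**Switch.** Under Section 5.2.4.2 a child on VKA starts edoxaban once the INR is 2.5 or lower: "This may occur as early as next day of the Extension Period". No latest day is given. Children on heparin start within hours of the last dose. The VKA target INR is 2.0 to 3.0 (Sections 5.2.1.2 and 5.2.4.3).

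**Main Treatment Period, for contrast.** Bleeding is counted from the date of first dose of study drug (Sections 2.3.1, 2.3.2 and 11.4.3.1).

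**The concern.** Five of the key secondary objectives in Section 2.1.2.1 assess edoxaban during the Extension: major plus CRNM bleeding, thromboembolism, all bleeding, death from thromboembolism, and all-cause mortality. Two features blur what the reported rates describe.

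First, the window is tied to a visit and not to the drug. A child with an INR of 2.6 to 3.0 at Month 3 is inside the VKA target but may not yet start edoxaban. A bleed or thromboembolic event while the INR falls belongs to the transition from SOC, yet it can appear in the edoxaban row. For a bleed, the same wait before a first edoxaban dose in the Main Treatment Period would not count as edoxaban time.

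Second, the single group mixes two exposures. Children from the SOC arm are in their first months on edoxaban. Children from the edoxaban arm have already had three months of it. If the risk of starting differs from the risk of continuing, the pooled rate describes neither, and the Extension's second look at starting edoxaban is diluted about two to one.

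**Working it through.** **The plan's own figure.** There is none for the Extension. The only precision statement is the Main Treatment Period interval in Section 11.6. It reproduces as an unpooled Wald interval: d = 0.085 − 0.103 = −0.018; SE = √(0.085×0.915/100 + 0.103×0.897/50) = 0.0512; d ± 1.96×SE = −11.8% to 8.2%. It does not bear on this point.

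**Inputs from the plan.** 100 edoxaban and 50 SOC subjects; Extension of up to 9 months plus 30 days, taken as 270 + 30 = 300 days.

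**Assumptions.** All 150 enter and all 50 SOC children have a gap, so both are ceilings. Gap lengths and hazard ratios are illustrative; the plan gives neither, and gives no VKA/heparin split.

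**1. Does Section 11.1 already close the gap?** Only in part.
- A child kept on SOC after the visit has not taken only edoxaban and falls outside the summary.
- A child who takes nothing while the INR falls has still taken only edoxaban in the Extension. Whether that child is summarised or listed turns on *right after*.
- Read loosely, pre-dose events enter the edoxaban rate. Read strictly, children with a higher INR at Month 3 drop out selectively.

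**2. How much time is involved?** Share = 50 × gap / [150 × (Extension days + 30)].
- 9-month Extension, denominator 150 × 300 = 45,000 person-days: 1 day gives 50/45,000 = 0.11%; 5 days gives 250/45,000 = 0.56%.
- 3-month Extension, denominator 150 × 120 = 18,000: 1 day gives 0.28%; 5 days gives 250/18,000 = 1.39%.

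If the event rate in the gap were five times the on-edoxaban rate, a 7-day gap would raise the pooled rate by 3.1% in relative terms (9-month Extension) or 7.8% (3-month).

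**3. What is one event worth?** In the pooled set the plan reports, 1/150 = 0.7 percentage points. Among 50 starters it would be 1/50 = 2 points, but the plan does not report that denominator.

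**4. What does pooling do?** Switchers are up to 50/150 = one third of the set. Suppose the hazard in the first three months on edoxaban is twice the later hazard, which is set to 1:
- starters' 9-month average = (3×2 + 6×1)/9 = 1.33;
- continuers' average = 1.00;
- pooled = (2/3)(1.00) + (1/3)(1.33) = 1.11;
- against continuers, 1.11/1.00 is +11%; against starters, 1.11/1.33 = 0.83, or −17%.

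If switchers' rate were instead a constant multiple of the continuers' rate throughout:

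| Switchers / continuers | Pooled / continuers | Pooled / switchers |
|---|---|---|
| 1 | 1.00 | 1.00 |
| 1.5 | 1.17 | 0.78 |
| 2 | 1.33 | 0.67 |
| 3 | 1.67 | 0.56 |

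**5. Is a split by arm already planned?** Sections 11.4.1.1, 11.4.1.2, 11.4.3.2 and 11.4.3.3 refer to summaries by treatment group for the Extension or the period after Month 3. Section 11.1 makes the Extension one edoxaban group, so those references do not clearly mean randomised arm.

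**The case against.** The strongest reply is that Section 11.1 already holds the safeguard: only children who take edoxaban alone are summarised, and late switchers are listed. The earliest permitted VKA switch coincides with the opening of the window, and heparin switches take hours, so for many children the gap is close to nil. This stands. A reader might infer that every former SOC child is counted as edoxaban before the first dose; the documents do not support that. Misattribution is a possibility at the margin.

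A reader might also infer that the window contradicts the rule assigning bleeds within 3 days of the last dose to the drug just stopped. It does not: that rule applies only when treatment is discontinued, and for children who complete Month 3 the Main Treatment Period ends at the visit in both arms. Nor are SOC events after that visit lost by mistake; the comparison ends there by design.

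The Extension results are descriptive, in a study stated not to be powered. Counting switching-phase bleeds against edoxaban can be called conservative for safety. That also stands, but it does not help a reader who wants the rate on edoxaban. With no randomised comparison in the Extension, no intention-to-treat reason requires starting at the visit.

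Section 11.7 leaves further definitions to a SAP. No separate SAP text is in the combined document, so it may settle this, but nothing available shows that it does.

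**Conclusion.** The point holds in a limited form. The window is anchored to the Month 3 Visit, so a pre-dose event in a former SOC child, mainly one leaving VKA, can be counted as an edoxaban event. Section 11.1 narrows this without removing it. The time involved is about 0.1–0.6% of the pooled total for gaps of 1–5 days under full 9-month entry; what is at stake is the attribution of single events, about 0.7 percentage points each in 150.

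Pooling is the larger part. Up to one third of the set are new starters, and no split by randomised arm is clearly planned. A reader might take the 11% and 17% differences as established distortions. They rest wholly on an assumed doubling of the early hazard and vanish if the rates are equal. It would also be wrong to describe the edoxaban-arm children alone as survivors, since switchers too must reach Month 3 and enter the Extension; the difference is prior edoxaban exposure. Because Extension entry is discretionary, and a global end-of-treatment date can shorten it, 50 of 150 is a planning figure and not a forecast.

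The primary comparison is unaffected. The change is still worth making, because it alters the rates reported for five key secondary objectives at little cost.

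**What to change.** Amend Sections 2.3.2, 2.3.3, 11.1, 11.4.1.1 and 11.4.3.1, and carry the wording into the SAP:

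1. For SOC-randomised subjects, start the Extension edoxaban window, for events and person-time alike, at the first edoxaban dose.
2. Tabulate events between the Month 3 Visit and that dose separately, as transition events.
3. Define *right after* in days for the Extension analysis set, and state how a child who takes no anticoagulant while waiting is classified.
4. Present Extension incidence and annualised rates by randomised arm (SOC-to-edoxaban and edoxaban-to-edoxaban), with the pooled figure alongside.

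These are counting and display rules only; the clinical switching procedure is not in question. The cost is wording and extra table columns. Randomised arm is known and drug administration is recorded (Section 5.4); confirm that the eCRF captures the first edoxaban dose date for switchers. The drawback is smaller denominators, at most about 50 and 100, so the separate rates will be less precise than the pooled one.

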2.3.1. Primary Safety Endpoint

The primary safety endpoint is a combination of major bleeding events and CRNM bleeding events per ISTH definition, occurring during the Main Treatment Period: from the date of first dose of study drug to the Month 3 Visit, or to the date of last dose of study drug plus 3 days if study treatment is discontinued, whichever is earlier.

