5.2.1.1. Edoxaban (Randomization through Month 12)

Edoxaban will be packaged and supplied to the subject on a monthly visit schedule as tablets (15 and/or 30 mg strength) or granules for oral suspension (60 mg strength) even though after Month 3 the clinic visitation schedule is every 3 months. For subjects who cannot pick up their study therapy on a monthly basis, accommodations will be made to allow the Investigator to distribute up to a 3-month supply of study drug to match the scheduled study visit interval.

Subjects will be instructed to take edoxaban (tablets or granules) orally once a day, at the same time every day, preferably in the morning, with or without food. One bottle of edoxaban granules will be used for each dosing day. Tablets should be swallowed with a glass of water.

The doses will be dispensed as follows:

For subjects 12 to <18 years old:

- A 60 mg dose will be dispensed as two 30 mg tablets or 10 mL from an individual bottle of oral suspension 60 mg
- A 45 mg dose will be dispensed as one 30 mg tablet plus one 15 mg tablet or 7.5 mL from an individual bottle of oral suspension 60 mg

- A 30 mg dose will be dispensed as one 30 mg tablet or 5 mL from an individual bottle of oral suspension 60 mg
- Doses provided by the granulation formulation will be dispensed with a dosing syringe according to the recommended dose shown in Table 5.1.
- If a subject does not have the capacity to swallow tablets in the 12 to <18 year and 6 to <12 year old groups, the tablets may be crushed and served with applesauce or mixed with 2 to 3 ounces of water and immediately administered by mouth or through an existing gastric tube, if needed.

For subjects 6 to <12 years old:

- 60 mg dose will be dispensed as two 30 mg tablets or as 10 mL from an individual bottle of oral suspension 60 mg.
- 45 mg dose will be dispensed as one 30 mg tablet plus one 15 mg tablet or as 7.5 mL from an individual bottle of oral suspension 60 mg.
- Dose other than 45mg and 60mg provided by the granulation formulation will be dispensed with a dosing syringe according to the recommended dose shown in Table 5.1. One bottle will be used for each daily dose.

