11.4.1.2. Exploratory Efficacy Analysis

The combination of symptomatic TE and asymptomatic intracardiac thrombus, deaths as a result of TE, and all-cause mortality will also be analyzed for periods and subjects below:

- Events from randomization to the date of last dose of study drug plus 30 days for subjects who do not participate in the Extension Period
- Events from the day after the Month 3 Visit to the data of last dose of study drug for subjects who participate in the Extension Period
- Events occurring from randomization to the Month 3 Visit or to the date of last dose of study drug plus 3 days if study treatment is discontinued in the Main Treatment Period, whichever is earlier.

To assess the efficacy for intra-patient between the Main Treatment Period and previous anticoagulant regimen, TE history since diagnosis of underlying disease and within the prior 3 months to randomization will be collected. The incidence of TE and annualized event rate in the 3 months prior to randomization and during the Main Treatment Period will be calculated for subjects who have both pre-randomization and post-randomization data available. This analysis will be based on Investigator-reported events.

To compare edoxaban regimen with available existing historical control data, a literature review and a search for registered clinical trials with similar endpoints will be conducted. The available results of control data will be extracted and tabulated together with the results of the Main Treatment Period from this study.

TE will also be classified as primary prevention events and secondary prevention events based on thrombosis history, and summarized by treatment group for events occurring during the Main

Treatment Period and from the day after the Month 3 Visit to the date of last dose of study treatment plus 30 days, respectively. Due to the small sample size of the study, further stratification by primary and secondary prevention is not feasible. Hence, caution is needed in the interpretation of the result, especially when imbalance occurred between two groups.

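### The supplementary Extension Period summaries close on the date of last dose with no added days, whereas the Main Period rule for subjects who discontinue adds 3 days

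*Combined protocol and SAP*

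**What the plan says.** Section 11.4.3.1 analyses three bleeding categories: major plus clinically relevant non-major (CRNM), major alone, and all bleeding. Its principal Extension analysis covers events "occurring from the day after Month 3 Visit to date of last dose of study drug plus 30 days in the Extension Period". That agrees with the secondary safety endpoint in Section 2.3.2, where the number of days added is also 30: "A combination of major and CRNM bleedings from the day after Month 3 Visit to the date of the last dose of study medication plus". Section 11.4.3.1 then adds a supplementary Extension summary of the same categories, covering "events occurring from the day after Month 3 Visit to the data of last dose of study drug for subjects who participate in" that period. I read the printed word data as date.

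Section 11.4.1.2 does the same for the TE composite, TE deaths and all-cause mortality: "Events from the day after the Month 3 Visit to the data of last dose of study drug". The next bullet in that list gives the Main Period version for the same endpoints: "Events occurring from randomization to the Month 3 Visit or to the date of last dose of study drug plus 3 days" for subjects who discontinue, whichever comes first.

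The 3-day rule also governs the primary endpoint. Section 2.3.1 counts bleeding "to the date of last dose of study drug plus 3 days if study treatment is discontinued", and Section 11.4.3.1 repeats it with the cap: "or to the date of last dose of study drug plus 3 days if study treatment is discontinued, whichever is earlier". Neither statistical section explains why the Extension summaries have no added days.

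**The concern.** A window that shuts on the date of last dose is shorter, and it is also selective. Section 5.6.1 names bleeding and TE among the situations in which study drug can be stopped permanently, and Section 5.6.3 lists major bleeding as a reason to discontinue. Under Section 9.1 a bleed can qualify as CRNM because it led to discontinuation of study drug. Take a bleed that starts during the night after a morning dose. If the child takes the next dose, the last-dose date moves later and the bleed is counted. If the bleed stops treatment, it falls one day outside the window and is not counted.

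All-cause mortality shows this most sharply. No dose can follow a death, so the last-dose mortality line can contain only deaths on the calendar date of the last dose. A child whose drug was held for a day or more before death is left out.

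At stake is the reading of a descriptive edoxaban-only rate for which the Extension Period has no comparator arm.

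**Working it through.** The plan gives no figure for this point, so there is none to reproduce. The check compares the windows and then gives one illustration.

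**Step 1: inputs**
- Supplementary Extension window: last dose + 0 days (Sections 11.4.1.2 and 11.4.3.1).
- Main Period window for discontinuers: last dose + 3 days, capped at the Month 3 Visit (Sections 2.3.1, 11.4.1.2 and 11.4.3.1).
- Secondary Extension endpoints: last dose + 30 days (Sections 2.3.2, 2.3.3, 11.4.1.1 and 11.4.3.1).
- Dosing: "orally once a day, at the same time every day, preferably in the morning" (Section 5.2.1.1). No clock time is fixed.
- Adverse events are collected to 30 days after the last dose (Section 9.2).

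**Step 2: apply each window as a date rule.** Count an event if (event date − last-dose date) ≤ g, with g = 0, 3 or 30. The cap at the Month 3 Visit is left aside.

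| Event date after last dose | g = 0 | g = 3 | g = 30 |
|---|---|---|---|
| Day 0 (same date) | counted | counted | counted |
| Days 1 to 3 | not counted | counted | counted |
| Days 4 to 30 | not counted | not counted | counted |

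The difference between the +0 and +3 rules is days 1 to 3 only.

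**Step 3: illustrative share.** Assume the last dose is at clock hour c, and that an event which prevents the next dose is uniformly timed over the following 24 hours. It falls on the next date if it starts after midnight, which has probability c/24.
- 06:00: 6/24 = 25%
- 08:00: 8/24 = 33%
- 10:00: 10/24 = 42%

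This is a share of stop-causing events, not of all events. If a fraction f of all events is of this kind, the under-count is f × c/24. The documents do not give f. Over its full range, 0 to 1, the under-count at these dose times runs from 0 to 42%.

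**Step 4: person-time.** The Extension lasts up to 9 months. At 30 days a month that is 270 days, so 3 further days add 3/270 = 1.1% for a child who completes it. The +0 rule can never give a higher event count than +3. If no event falls on days 1 to 3, the +3 rate is lower by a factor 270/273 = 0.989. If any do, the change in the numerator will usually be the larger.

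**The case against.** The strongest reply is that these summaries are extras. Section 11.4.1.2 is headed exploratory, the bleeding version in Section 11.4.3.1 is an additional summary, and no endpoint in Section 2.3 uses the last-dose window. A reader might infer that stop-causing events are lost from the study results. They are not, because every event on days 1 to 30 is in the secondary Extension endpoints. This stands and sets the priority.

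A reader might also infer that any event before the next dose is missed. That is too strong, because an event on the last-dose date itself is counted.

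A third inference would be that the cut-off could produce an apparent fall in bleeding from the Main to the Extension Period. The plan makes no such comparison. Section 6.4 confines treatment comparisons to the Main Period, and Section 11.1 summarises the Extension for edoxaban only. What remains is that the two rates are not defined alike if someone sets them side by side.

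The Main Period rule is also narrower than a flat 3 days. It applies only to discontinuers and is capped at the Month 3 Visit, so completers get no added days. Adding 3 days for every Extension child, including Month 12 completers, therefore does not copy it exactly. Under Section 17.7 another direct oral anticoagulant may begin 24 hours after the last edoxaban dose, so 3 days can include replacement-drug time. Both points stand. The second applies equally to the 3-day rule the plan already uses, and far more to the 30-day window.

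Finally, the numbers are small. If all 150 children entered the Extension and 8.5% bled (the adult rate used in Section 11.6), there would be 150 × 0.085 = 12.75, about 13 events, with an exact Poisson 95% interval of about 7 to 22. With an 08:00 dose and an assumed 30% to 50% of events ending treatment, the loss is 0.33 × 0.3 = 10% to 0.33 × 0.5 = 17%, or 1 to 2 events. That is well inside sampling error. It is still a one-directional loss of events, which an inexpensive change of wording removes.

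**Conclusion.** The point holds as a minor matter of consistency. The supplementary Extension summaries of bleeding, TE, TE death and all-cause mortality omit stop-causing events that begin on days 1 to 3 after the last dose. The plan's own rule for Main Period discontinuers would count them, subject to its cap. The omission can bias the last-dose rates low, in edoxaban's favour, and no reason is given for the difference.

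The size cannot be established from the documents. The 25% to 42% figure assumes a dose between 06:00 and 10:00, uniform onset over 24 hours, and an event that stops the next dose. It should not be read as an estimate of bias in the reported rate. The primary endpoint and the secondary endpoints, including those of the Extension Period, are unaffected.

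**What to change.** In the last bullet on bleeding periods in Section 11.4.3.1 and the second bullet of Section 11.4.1.2, end the window at the date of last dose plus 3 days. Apply the same end date to person-time. Leave the endpoints that run to last dose plus 30 days as they are. If the sponsor prefers to keep the last-dose cut-off, state the reason and note that it leaves out events that end dosing but start on a later date.

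No new data are needed, since events are already collected to 30 days after the last dose. Section 11.7 has the SAP finalised before database lock, and Section 15.4 allows a change in planned analysis to be documented in the SAP or a protocol amendment. The cost is up to 3 more days of person-time per child, possibly some time on a replacement anticoagulant, and perhaps a slightly less favourable descriptive rate.
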